11.1.4.2 Evaluation of Non-Target Lesions

Complete Response (CR): Disappearance of all non-target lesions and normalization of tumor marker level. All lymph nodes must be non-pathological in size (<10 mm short axis).

Note: If tumor markers are initially above the upper normal limit, they must normalize for a patient to be considered in complete clinical response.

Non-CR/Non-PD: Persistence of one or more non-target lesion(s) and/or maintenance of tumor marker level above the normal limits.

Progressive Disease (PD): Appearance of one or more new lesions and/or *unequivocal progression* of existing non-target lesions. *Unequivocal progression* should not normally trump target lesion status. It must be representative of overall disease status change, not a single lesion increase.

Although a clear progression of "non-target" lesions only is exceptional, the opinion of the treating physician should prevail in such circumstances, and the progression status should be confirmed at a later time by the review panel (or Principal

Investigator).

The duration of overall CR is measured from the time measurement criteria are first met for CR until the first date that progressive disease is objectively documented.

Duration of stable disease: Stable disease is measured from the start of the treatment until the criteria for progression are met, taking as reference the smallest measurements recorded since the treatment started, including the baseline measurements.

11.1.6 Progression-Free Survival

PFS is defined as the duration of time from start of treatment to time of progression or death, whichever occurs first.

11.1.7 Response Review

For Part 2 (the phase 2 portion) of the study, an expert(s) independent of the study will review all responses at the study's completion.

11.2 Antitumor Effect – Hematologic Tumors

N/A

11.3 Other Response Parameters

N/A

12. DATA REPORTING / REGULATORY REQUIREMENTS

Adverse event lists, guidelines, and instructions for AE reporting can be found in Section 7.0 (Adverse Events: List and Reporting Requirements).

12.1 Data Reporting

12.1.1 Method

This study will be monitored by the Clinical Trials Monitoring Service (CTMS). Information on CTMS reporting is available at http://www.theradex.com/CTMS. Data will be submitted to CTMS at least once every two weeks on the NCI/DCTD case report form or the electronic case report form (ACES).

12.1.2 Responsibility for Data Submission

N/A

12.2 CTEP Multicenter Guidelines

N/A

12.3 Collaborative Agreements Language

The agent(s) supplied by CTEP, DCTD, NCI used in this protocol is/are provided to the NCI under a Collaborative Agreement (CRADA, CTA, CSA) between the Pharmaceutical Company(ies) (hereinafter referred to as "Collaborator(s)") and the NCI Division of Cancer Treatment and Diagnosis. Therefore, the following obligations/guidelines, in addition to the provisions in the "Intellectual Property Option to Collaborator" (http://ctep.cancer.gov/industryCollaborations2/intellectual_property.htm) contained within the terms of award, apply to the use of the Agent(s) in this study:

1. Agent(s) may not be used for any purpose outside the scope of this protocol, nor can Agent(s) be transferred or licensed to any party not participating in the clinical study. Collaborator(s) data for Agent(s) are confidential and proprietary to Collaborator(s) and shall be maintained as such by the investigators. The protocol documents for studies utilizing Agents contain confidential information and should not be shared or distributed without the permission of the NCI. If a copy of this protocol is requested by a patient or patient's family member participating on the study, the individual should sign a confidentiality agreement. A suitable model agreement can be downloaded from: http://ctep.cancer.gov.

- 2. For a clinical protocol where there is an investigational Agent used in combination with (an)other Agent(s), each the subject of different Collaborative Agreements, the access to and use of data by each Collaborator shall be as follows (data pertaining to such combination use shall hereinafter be referred to as "Multi-Party Data"):
 - a. NCI will provide all Collaborators with prior written notice regarding the existence and nature of any agreements governing their collaboration with NCI, the design of the proposed combination protocol, and the existence of any obligations that would tend to restrict NCI's participation in the proposed combination protocol.
 - b. Each Collaborator shall agree to permit use of the Multi-Party Data from the clinical trial by any other Collaborator solely to the extent necessary to allow said other Collaborator to develop, obtain regulatory approval or commercialize its own Agent.
 - c. Any Collaborator having the right to use the Multi-Party Data from these trials must agree in writing prior to the commencement of the trials that it will use the Multi-Party Data solely for development, regulatory approval, and commercialization of its own Agent.
- 3. Clinical Trial Data and Results and Raw Data developed under a Collaborative Agreement will be made available to Collaborator(s), the NCI, and the FDA, as appropriate and unless additional disclosure is required by law or court order as described in the IP Option to Collaborator (http://ctep.cancer.gov/industryCollaborations2/intellectual_property.htm). Additionally, all Clinical Data and Results and Raw Data will be collected, used and disclosed consistent with all applicable federal statutes and regulations for the protection of human subjects, including, if applicable, the *Standards for Privacy of Individually Identifiable Health Information* set forth in 45 C.F.R. Part 164.
- 4. When a Collaborator wishes to initiate a data request, the request should first be sent to the NCI, who will then notify the appropriate investigators (Group Chair for Cooperative Group studies, or PI for other studies) of Collaborator's wish to contact them.
- 5. Any data provided to Collaborator(s) for Phase 3 studies must be in accordance with the guidelines and policies of the responsible Data Monitoring Committee (DMC), if there is a DMC for this clinical trial.
- 6. Any manuscripts reporting the results of this clinical trial must be provided to CTEP by the Group office for Cooperative Group studies or by the principal investigator for non-Cooperative Group studies for immediate delivery to Collaborator(s) for advisory review and comment prior to submission for publication. Collaborator(s) will have 30 days from the date of receipt for review. Collaborator shall have the right to request that publication be delayed for up to an additional 30 days in order to ensure that Collaborator's confidential and proprietary data, in addition to Collaborator(s)'s intellectual property rights, are protected. Copies of abstracts must be provided to CTEP for forwarding to Collaborator(s) for courtesy review as soon as possible and preferably at least three (3) days prior to submission, but in

NCI Protocol #: 9525

Version Date: July 22, 2022

any case, prior to presentation at the meeting or publication in the proceedings. Press releases and other media presentations must also be forwarded to CTEP prior to release. Copies of any manuscript, abstract and/or press release/ media presentation should be sent to:

Email: [contact]

The Regulatory Affairs Branch will then distribute them to Collaborator(s). No publication, manuscript or other form of public disclosure shall contain any of Collaborator's confidential/proprietary information.

13. STATISTICAL CONSIDERATIONS

13.1 Study Design/Endpoints

13.1.1 Part 1 (Phase 1b)

Part 1 (Phase 1b) of this study aims to determine the maximal tolerated dose (MTD) of trametinib and navitoclax that can be given safely in combination in order to determine a recommended phase 2 dose (RP2D). Patients with advanced or metastatic solid tumors that have been determined to harbor KRAS or NRAS mutations by CLIA-approved laboratory assay will be eligible. Prior therapy for advanced or metastatic disease will be allowed. Pharmacokinetic (PK) assays will be carried out to assess the interaction of these two drugs, and these data will be correlated with clinical toxicities as dose escalation is undertaken. Paired pre-treatment and ontreatment (day 15) tumor biopsies will be obtained to assess the pharmacodynamic response to therapy. Adverse events and DLT will be reported as defined in Sections 7 and 5.2, respectively. Evaluation of response rate will be performed as defined in Section 11.

Dose escalation will be conducted as outline in **Section 5.1**. The following table shows the probability of escalating the dose for various true, but unknown, rates of unacceptable toxicity.

True DLT Rate	Probability of Dose
	Escalation
10%	91%
20%	71%
30%	49%
40%	31%
50%	17%
60%	8%

13.1.1.1 Primary Objective

• To determine the dose-limiting toxicities of trametinib in combination with navitoclax, and the maximal doses at which both drugs can be safely administered together.

13.1.1.2 Primary Endpoint

Adverse events

13.1.1.3 Secondary Objectives

- To determine the pharmacokinetics of both drugs administered in combination.
- To assess for evidence of response to therapy.
- To evaluate the pharmacodynamic response to therapy in tumor biopsies.

13.1.1.4 Secondary Endpoints

- Pharmacokinetic Endpoints
 - o Maximum observed plasma drug concentration (Cmax)
 - Area-under-the concentration-time-curve from zero (pre-dose) to 24 hours (AUC(0-24)) for trametinib and navitoclax when administered in combination.
 - o pre-dose (trough) drug concentration at the end of the dosing interval for trametinib and navitoclax when administered in combination.
 - o t1/2 of trametinib and navitoclax when administered in combination.
- Response rate (partial response [PR] + complete response [CR])
- Pharmacodynamic Endpoints: Change in levels (between pre-treatment and day 15 tumor biopsies) of proteins/mRNAs implicated in MAPK or BCL2 family signaling, proliferation markers (Ki67), or apoptosis markers (Cleaved caspase-3)

13.1.2 Part 2 (Phase 2)

Part 2 is a single-arm Phase 2 study of trametinib in combination with navitoclax at the RP2D determined in the Phase 1b trial above. Patients with KRAS or NRAS mutation-positive solid tumors will be enrolled into up to 4 different disease-specific expansion cohorts. These will include expansion cohorts for patients with KRAS or NRAS mutation-positive: (1) Pancreatic cancer, (2) GYN cancer, (3) lung cancer, (4) all other solid tumor types exclusive of pancreatic, GYN, and lung cancers. Part 2 aims to evaluate the efficacy of this regimen in the tumor types above and to further evaluate the safety and toxicity profile of this regimen at the RP2D defined in Part 1 of the study. Paired pre-treatment and on-treatment (day 15) tumor biopsies will be obtained on the first 15 patients enrolled in Part 2 (minimum 4 patients biopsied in each of expansion cohorts 1, 2, and 3) to assess the pharmacodynamic response to therapy. Adverse events will be reported as defined in Section 7. Evaluation of response rate will be performed as defined in Section 11. PFS will be determined as defined in Section 11.1.6.

NCI Protocol #: 9525

Version Date: July 22, 2022

The primary goal of Part 2 is to evaluate the efficacy of this regimen in patients with various KRAS or NRAS mutation-positive solid tumor. Based on traditional response rates to standard second line chemotherapy in the tumor types being studied (Guglielmi et al, 2007; Conroy et al, 2011), we conclude that a response rate of 15-20% or greater in a given expansion cohort would deem this regimen worthy of further study in that specific patient population. In part 2, patients will be enrolled in 4 expansion cohorts by a two-stage design, as outlined in Section 5.1. Initially 12 patients will be enrolled to each cohort in Stage 1. If no responses are observed in a given cohort among the first 12 patients, then that cohort will be stopped for futility. However, if one or more responses are observed in a given cohort, the cohort will proceed to Stage 2, and an additional 13 patients will be enrolled for a total of 25 patients in that cohort. If at least three responses are observed within a completed cohort of 25 patients, the regimen will be considered promising for treating the specific tumor type. This design has a 11% false-positive and a 22% false-negative error rate for testing a 17% vs. a 5% response rate. The probability of early stopping is 54% if the underlying response rate were truly only 5%. In the event that the number of responses observed in a given cohort does not meet the pre-established response criteria defined above, but promising anti-tumor activity is observed (such as prolonged stable disease or tumor regressions that fall short of the RECIST cutoff for partial response), the possibility of further evaluating of this regimen in the specific patient population can be explored through a joint discussion between the investigators, pharmaceutical collaborators, and the NCI-CTEP.

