5.1.1 Treatment plan for Part 1 (Phase 1b)

Dosing levels for Part1 of the study are listed below in **Table 5.1** and dose escalation will proceed as outlined in Figure 5.1. Agents will be dosed daily in a 28-day cycle according to the description outlined in Table 5.2. A 28-day cycle has been used in previous combination studies with trametinib, such as the study combining trametinib and dabrafenib, summarized in section 2.2.1.4. Subjects will be assessed for toxicities and safety at weekly intervals during the first 28day cycle, at two week intervals during cycle two, and monthly thereafter. Subjects will undergo radiographic assessments of tumor response every 2 cycles (8 weeks +/- 1 week). The schema for dose escalation is shown below in **Table 5.3**, utilizing standard Phase 1 cohorts of 3 subjects per dose level. The occurrence of 1 dose limiting toxicity (DLT; defined in Section 5.2) will prompt expansion of a given dose level to 6 subjects. The occurrence of 2 DLTs in a given dose level will indicate that the maximal tolerated dose (MTD) has been exceeded, and expansion of the prior dose level to 6 subjects will occur, if not already performed. Patients will be replaced if they are not evaluable for the DLT window. The dose of each agent to be used for Part 2 (Phase 2) of the study (the recommended Phase 2 dose (RP2D)) will be the highest dose level at which no more than 1 subject out of 6 experiences a DLT. Dose escalation will proceed until the MTD/RP2D have been determined, or until the RP2D of each compound individually (2mg daily for trametinib; 325mg daily for navitoclax) is reached (represented by dose level 7). If the MTD is reached before dose level 7, alternative dosing schemes will be considered by the investigators in which trametinib is dosed intermittently in an effort to reduce toxicity (denoted as Schedule C). If necessary, the exact details of these alternative dosing schemes will be designed at a future date through a protocol amendment.

[figure not shown]
Table 5.1: Dosing Levels for Part 1 (Phase 1b)

	Dose Escalation Levels	3
]	Dose
Dose Level	Trametinib	Navitoclax
	(mg) PO daily	(mg) PO daily
Level 1	1	150

Level 2	1.5	150
Level 3*	1.5	200
Level 4*	2	200
Level 5*	2	250
Level 6*	2	300
Level 7*	2	325

^{*}Dose levels 3-7 will include a 7-day lead-in dosing period for navitoclax at 150 mg PO daily.

Figure 5.1: Dose Escalation Schema for Part 1 (Phase1b)

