Dose levels 1-3 will be enrolled according to Schedule A (i.e. dosing cohorts 1A, 2A, 3A). After completion of dose level 3A, if dose escalation is warranted per the criteria outlined in Table 5.3 above, an investigator meeting will be held with NCI/CTEP and pharmaceutical collaborators to review safety data. Pharmacokinetic data will be reviewed to evaluate for any evidence of drug interaction, and adverse event data will be reviewed to evaluate for any potentiation of toxicity (in particular, thrombocytopenia) by the combination. If significant safety concerns are noted, dose escalation will proceed for the remainder of the study according to Schedule A (i.e. to dosing cohort 4A, 5A, 6A, 7A). If no significant safety concerns are noted, and it is deemed safe to proceed, dosing will return to dose level 1 according to schedule B (i.e. dosing cohort 1B). Dose escalation will then proceed according to Schedule B to dosing cohort 3B. Since both dose levels 2 and 3 involve beginning with 150 mg navitoclax and 1.5 mg trametinib, it is not necessary to evaluate dose levels 2 and 3 both according to schedule B, as both would test the safety of initiating navitoclax and trametinib simultaneously at these same doses. Therefore, dose escalation will proceed directly from cohort 1B to cohort 3B. If >1 DLT is experienced within dosing cohort 1B or within 3B, then Schedule B will be abandoned, and dose escalation will proceed with dosing cohort 4A. If dosing cohort 3B is completed with ≤1 DLT, then a second investigator meeting will be held with NCI/CTEP and pharmaceutical collaborators to review safety data. Pharmacokinetic data will be reviewed to evaluate for any evidence of drug interaction, and adverse event data will be reviewed to evaluate for any potentiation of toxicity (in particular, thrombocytopenia) by the combination. If the investigators and NCI/CTEP and pharmaceutical collaborators agree that Schedule B demonstrates a comparable or improved safety profile relative to Schedule A, then dose escalation will proceed according to Schedule B (i.e. to dosing cohort 4B, 5B, 6B, 7B) until the RP2D is determined. However, if evidence of drug interaction exists, or if the investigators and NCI/CTEP and pharmaceutical collaborators agree that Schedule A demonstrates a superior safety profile, particularly as it relates to navitoclax-associated thrombocytopenia, then dosing will proceed for the remainder of the study according to Schedule A (i.e. to dosing cohort 4A, 5A, 6A, 7A) until the RP2D is determined. If, however, unacceptable toxicity (either >1 DLT or toxicity not meeting criteria for DLT, but deemed to be unacceptable by investigators) is observed at a given dose level independent of schedule A or B, then and alternative dosing schedule (Schedule C) will be explored with intermittent trametinib dosing (days 1-14 only of each 28 day cycle), beginning at the last dose level completed. With Protocol Version 10 (dated 8/9/16), there will be no further Dose Escalation on Schedule A or B.

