
Table 5.2: Schedule of Agent Administration

Schedule A and B:

	Reg	gimen Desc	ription		
Agent	Premedications; Precautions	Dose	Route	Schedule	Cycle Length
Trametinib	Take on empty stomach, >1 hour before meal or >2 hours after meal	** tablet(s)	PO daily, >1 hour before meal or >2 hours after meal	Days 1-28	28 days (4 weeks)
Navitoclax*	Take with food.	** tablet(s)	PO in the a.m.	Days 1-28	

^{*} For days on which subjects will undergo an on-treatment biopsy, Navitoclax should be taken in the a.m. with Jello at least two hours before the scheduled biopsy.

Schedule C:

	Reg	gimen Desc	ription		
Agent	Premedications; Precautions	Dose	Route	Schedule	Cycle Length
Trametinib	Take on empty stomach, >1 hour before meal or >2 hours after meal	** tablet(s)	PO daily in the p.m., >1 hour before meal or >2 hours after meal	Days 1-14	28 days (4 weeks)
Navitoclax*	Take with food.	** tablet(s)	PO in the a.m.	Days 1-28	

^{*} For days on which subjects will undergo an on-treatment biopsy, Navitoclax should be taken in the a.m. with Jello at least two hours before the scheduled biopsy.

Table 5.3: Dose Escalation Criteria for Part 1 (Phase 1b)

Number of Patients with DLT at a Given Dose Level	Escalation Decision Rule
--	---------------------------------

^{**}Doses as appropriate for assigned dose level.

^{**}Doses as appropriate for assigned dose level.

0 out of 3	Enter 3 patients at the next dose level.
≥2	Dose escalation will be stopped. This dose level will be declared the maximally administered dose (highest dose administered). Three (3) additional patients will be entered at the next lowest dose level if only 3 patients were treated previously at that dose.
1 out of 3	 Enter at least 3 more patients at this dose level. If 0 of these 3 patients experience DLT, proceed to the next dose level. If 1 or more of this group suffer DLT, then dose escalation is stopped, and this dose is declared the maximally administered dose. Three (3) additional patients will be entered at the next lowest dose level if only 3 patients were treated previously at that dose.
≤1 out of 6 at highest dose level below the maximally administered dose	This is generally the recommended phase 2 dose. At least 6 patients must be entered at the recommended phase 2 dose.

Patients will be replaced if they are not evaluable for the DLT window.

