Patients will be enrolled to each expansion cohort according to the schema below. A total of 12 patients will be enrolled in each expansion cohort. If no objective tumor responses (partial or complete responses, as defined in section 11.1.4) are seen in the first 12 patients enrolled in a given cohort, the cohort will close. If at least one objective tumor response is observed in a given cohort, an additional 13 patients (for a total of 25 patients) will be enrolled to that cohort. Statistical considerations are discussed in more detail in Section 13. Patients will be assessed weekly for toxicity and safety during the first 28-day cycle and monthly thereafter. Patients will undergo radiographic assessment of tumor response every 2 cycles (8 weeks).

Part 2 (Phase 2)

Version Date: July 22, 2022

Stage 2:	Stage 2:	Stage 2:	Stage 2:
Enroll 13	Enroll 13	Enroll 13	Enroll
Patients	Patients	Patients	Patients
N = 25 total			

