13.1.2.1 Primary Objectives

- To determine the response rate of the combination of trametinib and navitoclax in subjects with KRAS or NRAS mutation-positive advanced or metastatic solid tumors in disease-specific expansion cohorts.
- To confirm the safety and tolerability of trametinib and navitoclax in combination at the RP2D determined in the Phase 1b portion.

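### Part 2 has a primary objective of confirming safety at the RP2D, but no cumulative toxicity count requires the RP2D to be reviewed

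*Combined protocol and SAP*

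**What the plan says.** Part 2 has two primary objectives (1.1.2 and 13.1.2.1): the response rate in each cohort, and "To confirm the safety and tolerability of trametinib and navitoclax in combination at the RP2D determined in the Phase 1b portion". Section 13.1.2.2 lists adverse events among the primary endpoints. The opening of 13.1.2 words the safety aim more softly, as to "further evaluate the safety and toxicity profile of this regimen at the RP2D defined in Part 1 of the study", and then calls efficacy the primary goal.

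The cohort rules in 5.1.2 and 13.1.2 use response only. At stage 1: "If no responses are observed in a given cohort among the first 12 patients, then that cohort will be stopped for futility". At the end: "If at least three responses are observed within a completed cohort of 25 patients, the regimen will be considered promising".

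Counted toxicity rules appear in Part 1 only. The RP2D "will be the highest dose level at which no more than 1 subject out of 6 experiences a DLT", and Table 5.3 adds: "At least 6 patients must be entered at the recommended phase 2 dose". Part 1 also convenes reviews: after level 3A, if escalation is warranted, "an investigator meeting will be held with NCI/CTEP and pharmaceutical collaborators to review safety data", with a second such meeting after 3B.

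For Part 2 the documents provide:
- scheduled checks (5.1.2): "Patients will be assessed weekly for toxicity and safety during the first 28-day cycle and monthly thereafter"
- patient-level dose changes (Section 6)
- expedited reporting of serious events to NCI (7.3)
- data submission at least every two weeks (12.1.1)
- a general duty on the Protocol Chair to review adverse events (Appendix B)

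None of these sets a cumulative count or rate.

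**The concern.** An objective to confirm safety needs some result that would count as failure to confirm. Part 2 states none. Part 1 says what happens at 2 DLTs in a dose level. Part 2 enrols many more patients, yet does not say how many such events should bring the dose back for review.

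What is at stake is the timing of that review. The RP2D may rest on as few as 6 patients at that dose, plus neighbouring levels among the 21 to 30 expected in Part 1 (13.2.1). Part 2 then enrols 48 to 100 (13.2.2). If the dose is too toxic, whether and when it is reconsidered depends wholly on someone judging that the reports have become too many.

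**Working it through.** **The plan's own figures.** The two-stage response rule (stop at 0/12, promising at 3 or more of 25):
- Early stopping at 5%: 0.95^12 = 0.540 (stated 54%).
- Probability of a promising result: sum over x = 1 to 12 of Bin(x; 12, p) × P(at least 3 − x responses in 13). This is 0.114 at p = 5% (stated 11%). At p = 17% it is 0.781, so the false-negative rate is 0.219 (stated 22%).

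The Part 1 escalation table in 13.1.1, with q = 1 − p: q^3 + 3pq^5 gives 90.6, 70.9, 49.4, 30.9, 17.2 and 8.2% at DLT rates of 10 to 60% (stated 91, 71, 49, 31, 17, 8). All match. The issue is an omission, not a wrong number.

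**How firmly 6 patients fix the RP2D.** P(at most 1 of 6) = q^6 + 6pq^5:
- 30%: 0.118 + 0.303 = 0.420
- 40%: 0.047 + 0.187 = 0.233
- 50%: 0.016 + 0.094 = 0.109

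These are chances that a level with that rate meets the criterion, not chances that Part 2 runs at such a dose. They are upper bounds, because 5.1.1 lets investigators find toxicity unacceptable below the DLT threshold and Table 5.3 says only that the criterion generally gives the RP2D. After 1 DLT in 6, the exact 95% interval for the rate is 0.4% to 64%.

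**A worked trigger.** The ceiling c, prior, cutoff and looks are illustrative choices, not taken from the documents. The limit at each look is the smallest x with P(rate > c | x of n) > 0.90, under a Beta(2c, 2 − 2c) prior. For c = 0.30 and n = 12, x = 5 gives Beta(5.6, 8.4) and 0.772; x = 6 gives Beta(6.6, 7.4) and 0.905. The first limit is therefore 6.

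| Patients | 12 | 24 | 36 | 48 | 60 | 72 | 84 | 100 |
|---|---|---|---|---|---|---|---|---|
| 30% ceiling | 6 | 11 | 15 | 19 | 23 | 27 | 31 | 37 |
| 25% ceiling | 6 | 10 | 13 | 17 | 20 | 24 | 27 | 31 |

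Probability of a pause by 100 patients, by exact sequential binomial calculation over these looks:

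| True rate | 20% | 25% | 33% | 40% |
|---|---|---|---|---|
| 30% ceiling | 2% | 9% | 46% | 87% |
| 25% ceiling | 5% | 22% | 79% | 98% |

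Detection takes time. With the 30% ceiling and a true 40% rate, the pause probability is P(at least 6 of 12) = 0.335 at the first look and 0.680 by 48 patients.

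**Lag.** At 8 to 10 patients a month (13.2.2), 8 × 42/30.4 = 11 to 10 × 42/30.4 = 14 more patients enrol while each 42-day window completes.

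**The case against.** The best defence is that Part 2 is already supervised. Grade 3 to 5 serious events generally go to NCI within 24 hours, data arrive at least every two weeks, and the Protocol Chair must review adverse events. Section 13.1.2 calls efficacy the primary goal and speaks of further evaluating safety, so the endpoint could be met by description. No cohort passes 12 patients without a response. This is why the point is an improvement rather than a fatal flaw. It does not supply the missing element, because none of these duties says what count requires the dose itself to be reviewed, and 13.1.2.1 says confirm.

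A reader might infer that a cohort can be called promising regardless of toxicity. The documents do not support that. Under 13.5.2, deaths from toxicity are treatment failures and patients who stop early stay in the main analysis, so both count as non-responders unless they responded first. Severe toxicity therefore already weighs on the response count, though only indirectly.

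A reader might also apply a high DLT rate to all 48 to 100 patients and project a total. That would assume a rate the documents do not give, and that nobody acts on the reports.

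Two criticisms of the example stand. It still ends in judgement; what it adds is a mandatory, recorded review at a known point. And its limits are a matter of choice: 5 of 12 (42%) does not pause enrolment, whereas Part 1 treats 2 DLTs at a level as exceeding the MTD. Limits built on an assumed acceptable rate of 20% (6/12, 9/24, 15/48) would trigger 93% of the time by 48 patients at a true 40% rate, against 68% here, at the price of 7% rather than 2% at a true 20% rate.

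**Conclusion.** The gap is real and worth closing. Part 2 has a primary safety objective and response-only decision rules, and no cumulative toxicity count requires a review of an RP2D that may rest on 6 patients. The 42%, 23% and 11% follow exactly from the stated criterion if 6 patients are tested at that level, and are upper bounds on a level of that toxicity being accepted. It would be wrong to say that Part 2 lacks safety monitoring; what it lacks is a defined trigger. That finding does not depend on the ceiling, prior or cutoff in the example. The example's operating characteristics do, and they describe the first pause only.

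**What to change.** Add to 13.1.2, with the sponsor setting the ceiling and hence the limits:

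> Toxicity is monitored across all Part 2 cohorts combined. Events meeting Section 5.2 with onset within 42 days of first dose are counted, one per patient, by onset date. [State whether only events at least possibly related under 7.2 count.] A patient is evaluable once followed for 42 days or once such an event occurs; patients are taken in order of first dose. If the number of patients with an event reaches the limit at any look, new enrolment pauses until the Protocol Chair and NCI-CTEP have reviewed the RP2D and recorded a decision. Accrual is not otherwise held. The toxicity outcome is reported beside any promising verdict.

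Three details need care. Section 5.2 addresses attribution only for bleeding and counts any grade 4 toxicity, so without a relatedness rule disease events could trigger pauses. Onset date matters because C2D15 is day 43 (28 + 15) and Section 10 allows 3 days either side. The evaluability wording is needed because 13.5.1 counts every treated patient and replacement for the DLT window is stated only for Part 1.

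The cost is one paragraph and a small table, using the existing event definition, reviewers and visits. The downsides are an occasional unnecessary pause (2% at a true 20% rate and 9% at 25% with the 30% ceiling; 5% and 22% with the 25% ceiling) and the 11 to 14 patients who enrol during each window.
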